#### **K.6. Outcome Measures (Pilot and General Studies):**

**Data Collection Methods (General Study):** In order to enhance the reliability of the data collection and analysis process, the web-based software toolset REDCap (Research Electronic Data Capture) will be utilized in this study. REDCap is a secure, web application designed for electronic collection, management, and storage of clinical research data. The system includes features for HIPAA compliance including real-time data entry validation (e.g., for data types and range checks), a full audit trail, user-based privileges, de-identified data export mechanism to numerous statistical packages (e.g., SPSS, SAS, Stata, and R), and integration with the institutional Active Directory. REDCap is also compliant with FDA requirements, and hence is the ideal system of this FDA-supervised study (see Section M.4 for details). Notably, REDCap@Yale is being used in VA HSS-approved protocols (e.g., HSS #1586389), and the version of REDCap used in the current study has several additional layers of safety, due to its compliance with FDA requirements (please see section M.4. for details).

Following informed written consent, participants will be assigned a unique study ID, which will be used across all REDCap surveys during both screening and experimental sessions. Once in the database,

participants will only be able to complete surveys via a scannable QR code provided by a research assistant. All REDCap data collection will be done on Yale-managed iPads. Only personable identifiable information (PII) (e.g.) email, age in years, and sex/gender) will be collected, no personal health information (PHI) will be entered into REDCap. Assisted by study staff, participants will have the option of using a study-specific email, rather than their personal email.

The option to use traditional paper-survey's will be provided if participants prefer not to use computerized behavioral data collection.

### Experimental Session Measures

#### Safety Assessments

**Screening for alcohol intoxication:** Before the start of each session, participants will be screened for alcohol intoxication by clinical examination (e.g., neurological exam and field test) and laboratory assessment (urine ethyl glucuronide testing). The use of breathalyzers will be limited due to the risk of exposure to SARS-CoV-2 through aerosols.

**Systematic Assessment of Side Effects (SAFTEE):** To monitor adverse events from the study medications, the SAFTEE will be administered before and after each experimental session. This is a symptom checklist that has been used successfully in our previous studies to assess possible side effects of study medications. It includes information regarding severity of any presenting side effects, as well as the course of action taken by study staff in response.

**Vital Signs:** Heart rate, respiratory rate, blood pressure and pulse oximetry will be monitored throughout the session.

**Neuropsychological battery:** For cognitive performance, we chose tests that are likely to be sensitive to CBD's effects in our patient sample, such as the Continuous Performance Test (CPT) and the HVLT (Hopkins Learning Verbal Test). *Continuous Performance Test (CPT)* – will assess attention, concentration, and working memory. The outcomes will be percent correct responses and reaction time. *Hopkins Verbal Learning Test (HVLT)* – will measure verbal memory. The outcome will be delayed recall. Both the CPT and HVLT have been used to measure cognitive performance in prior studies with CBD.

**Opioid Withdrawal Symptom Checklist (OWSC):** This instrument will measure opioid withdrawal symptoms.

**Drug Effects Questionnaire (DEQ):** Participants will rate the following items from "not at all" to "extremely" on a 100-mm scale: "alert," "calm," "confused," "depressed," "confused," "high," "anxious," "sedated," "tired," "social," "self-confident," "talkative," "hungry," "feeling the drug strength," "feel good drug effects," "feel bad drug effects," and "want more drug." These items are commonly used to assess effects of drugs.

**Mini Mental Status Examination (MMSE):** The Mini-Mental State Examination (MMSE) or Folstein test is a 30-point questionnaire that is used extensively in clinical and research settings to measure cognitive impairment.

**Agitation Calmness Evaluation Scale (ACES):** The ACES consists of a single item that rates overall agitation and sedation at the time of evaluation, where 1 indicates marked agitation; 2, moderate agitation; 3, mild agitation; 4, normal behavior; 5, mild calmness; 6, moderate calmness; 7, marked calmness; 8, deep sleep; and 9, unarousable. The ACES is a well-validated instrument to assess sedation and has been used in various clinical trials.

**Field Test:** The field test will consist of a finger-to-nose test; a walk-and-turn test; a Romberg test. During the *finger-to-nose test*, participants will be asked to bring tip of the index finger up to touch the tip of the nose while his/her eyes are closed and his/her head is tilted slightly back, six times – three with each hand. During the *walk and turn test*, participants will be asked to take nine heel-to-toe steps along a straight line. After taking nine heel-to-toe steps, participants will then be directed to turn on one foot

and return in the same exact manner in the opposite direction. During the *Romberg test*, participants will be asked to stand with their feet together, head tilted back, and eyes closed for 30 seconds. The study physician will look for clues of changes from baseline, such as any loss of psychomotor coordination, loss of balance, eyelid/body tremors, muscle tone, and ability to follow directions.

**Positive and Negative Affect Schedule (PANAS)**: This is a 20-item, widely used measure of momentary mood states, has been found to be sensitive to the mood-altering effects of several substances .

Its reliability and validity have been extensively evaluated (Ref). The PANAS consists of 20 emotion words, with 10 loading on the Positive Affect factor and 10 on the Negative Affect factor (10). Sample words for Positive Affect include “alert”, “inspired”, and “enthusiastic”. Sample words for Negative Affect include “distressed”, “upset”, and “guilty”. Participants rate the degree to which they endorse each item on a rating scale (1 = very slightly or not at all; 5 = extremely). Items are then totaled to create a score for each factor: Positive Affect and Negative Affect. Higher scores represent greater endorsement of the construct. High levels of The PANAS will be used during each session and at each weekly outpatient session to measure the effects of CBD on mood.

## **Pain Assessments**

**Brief Pain Inventory – Short Form (BPI-SF)**: The BPI-SF is a self-report questionnaire that assesses severity of pain, impact of pain on daily function, location of pain, pain medications, and amount of pain relief in the past 24 hours or the preceding week . It will be used during screening and before experimental sessions.

**Quantitative Sensory Testing (QST) of Thermal Pain**: This is a reliable, dynamic, and computerized method of quantifying distinct mechanisms of the pain experience, measuring top-down pain inhibition and bottom-up pain facilitation (**Figure 4**). QST measures are sensitive to the effects of cannabinoids , important biomarkers of chronic pain, and predictors of the pain treatment response .

**Conditioned Pain Modulation (CPM)**: CPM measures top-down pain inhibition, by leveraging the “pain inhibits pain phenomena”. Higher CPM reflects supra-spinal pain modulation .

**Temporal Summation of Pain (TSP)**: TSP involves the repeated administration of noxious stimuli, indexing bottom-up pain facilitation . Higher TSP indicates the increased firing of ascending pre-synaptic neurons, reflecting mechanisms of central sensitization.

**Pain Visual Analog Scale (VAS)**: The pain VAS will be used by participants as a secondary rating scale for pain severity before, during, and after pain testing. This scale contains a horizontal line, anchored by verbal descriptors of “no pain” and “pain as bad as it could be”. Participants will place a vertical line at the point that best indicates their present pain .

**Pain Catastrophizing Scale (PCS)**: This is a 13-item self-report scale to measure pain catastrophizing. Each item is rated on a 5-point scale: 0 (Not at all) to 4 (all the time). It contains three subscales: magnification, rumination, and helplessness .

## **Craving and Attentional Bias Assessments**

**Heroin Craving Questionnaire (HCQ-14)**: This instrument will measure cue-induced urges to use heroin, which are highly relevant for persons with comorbid OUD and chronic pain receiving opioid agonist maintenance .

**Opioid Attentional Bias (AB)**: The primary AB measure will be a visual probe (VP) task . VP tasks rely on a tendency for individuals to respond faster to probes (e.g., small dots) when they are presented in an attended region of a visual display. In the task used in this study, a drug-related word is presented next to a neutral word for 500 milliseconds. Subsequently, a probe (e.g., a dot) replaces the drug word or the neutral word. The participant’s task is to indicate the location of the probe as quickly as possible by pressing one of two buttons on the mobile device. Faster responses when the probe replaces the drug word is interpreted as an AB to drug cues. A drug Stroop task will also be used to assess generalization of training effects to a second AB measure. Drug Stroop tasks are a form of emotional

Stroop widely used in addiction studies. Longer latency to name the color of a word when it is a drug word compared to when it is a neutral word is indicative of an AB to drug words. For all AB tasks, opioid words will be presented in separate blocks in counterbalanced order. As in our Preliminary Studies, neutral words are common indoor/ household (e.g., couch) and outdoor items (e.g., fence) equivalent to the cocaine (e.g., smoke) and opioid words (e.g., smack) in length and frequency of use in the English language. For opioid words, we focused on both heroin and prescription opioid medications. Immediately before and after the opioid dot probe task participants will be asked estimate *cue-elicited craving* with a VAS. The difference of these ratings will be used to index cue-elicited craving.

#### Intake and Follow-up Measures

**Timeline Follow-Back Assessment Method (TLFB)**: Drug use for the past 30-day period prior to study, participation and throughout the period of study participation will be obtained using this self-report measure. Participants are given a blank calendar covering the specified time interval and are asked to retrospectively reconstruct their drug use over that time interval. The process is facilitated by establishing anchor points (e.g., holidays, anniversaries, major national events, etc.). It can be scored to provide the number of days on which various levels of drug use occurred. The time-line method has good test-retest reliability and good validity for verifiable events. It has been used in numerous studies to assess substance use.

**Childhood Trauma Questionnaire (CTQ)**: This is one of the most sensitive tools for quantifying early maltreatment, and it measures five categories of childhood maltreatment: Emotional, Sexual and Physical Abuse (EA, SA and PA), and Emotional and Physical Neglect (EN and PN). Scores on the CTQ, specifically, correlate with both the onset and course of mental illness, As well as the structure, function and connectivity of critical brain regions associated with resilience and vulnerability to life stressors (i.e., amygdala). This outcome measure will be included in the intake session because of the potential role of trauma as moderator of the cannabinoid and opioid response.

**Hamilton Depression Rating Scale (HDRS)**: The HDRS is the one of most widely used clinician-administered depression assessment scale. The original version has 17 items pertaining to symptoms of depression experienced over the past week. This instrument will be used to assess depressive symptoms during screening. Candidates who meet criteria for severe depression will be excluded and referred for treatment.

**Columbia Suicide Severity Rating Scale (C - SSRS)**: The C-SSRS is a measure used to identify and assess individuals at risk for suicide. Participants with active suicidal ideation will be excluded from the study and referred for treatment.

**K.7. Biological Specimen Collection / Phlebotomy (Pilot and General Studies)**: Biological specimens will be collected at baseline for safety/routine lab work, as well as to examine the effect of administration of CBD on serum methadone/buprenorphine levels, since these drugs are CYP450 3A4 substrates (**Table 2**). Further, we will collect potential biomarkers, including cytokines (TNF-alpha, IL-6, and IL-10) and endocannabinoid levels (e.g., 2-Arachidonoylglycerol and anandamide) for exploring the relationship between cannabinoid therapeutics, analgesia, and opioid-mediated inflammation. Your information or biospecimens collected as part of the research, even if identifiers are removed, will not be used, or distributed for future studies.

There will be a total of five blood draws in this study, one at screening and four at each test session. Over the course of the study, less than 175 ml (3/4 of a cup) of blood will be drawn. Participants may choose to not have blood draw during the testing sessions, and therefore not have an IV catheter placed. Those who choose not to have an IV placed during the test sessions, will have just safety bloods drawn 80ml (1/3 of a cup) over the course of four test sessions. Notably, the amount of blood drawn at screening and on each of the study visit is well within the Red Cross blood standards.

**K.8. Schedule of Study Visits (Pilot and General Studies):** Participants will have the following visits (Table 1A and 1B):

Table 1A. Experimental Design for the Pilot Study				
Day 0	Day 1	Day 4	Day 7	Day 14
IS Lab Assessments	ES	ES	ES Lab Assessments	FU

**Day 0:** Screening.

**Day 1:** First experimental session, where the first dose of study medication will be administered, and laboratory experiments will be conducted.

**Day 4:** Second experimental session.

**Day 7:** Third experimental session.

**Day 10:** Follow-up telephone contact.

Table 1B. Experimental Design for the General Study					
Day 0	Day 1	Day 4	Day 7	Day 10	Day 17
IS Lab Assessments	ES	ES	ES	ES Lab Assessments	FU

Abbreviations: *IS*: Initial Screening; *ES*: Experimental Session; *FU*: Follow-up telephone contact

**Day 0:** Screening.

**Day 1:** First experimental session, where the first dose of study medication will be administered, and laboratory experiments will be conducted.

**Day 4:** Second experimental session

**Day 7:** Third experimental session.

**Day 10:** Fourth experimental session.

**Day 17:** Follow-up telephone contact.

Timepoint	Measures and Events
Baseline	VS, physical exam, ACES, MMSE, field test, Lab Assessments, EKG, SOWS, breathalyzer, urine drug testing, plasma opioid (methadone/buprenorphine) level, TLFB, SAFTEE, DEQ, CPT, HVLT, PANAS, AB, HCQ-14, PCS
0 min *	Cannabidiol (400, 800, 1200 mg) or placebo* administration
30 min	VS, SOWS, DEQ, PANAS
60 min	VS, DEQ, PANAS
90 min	VS, SOWS, cue session, AB, HCQ-14, pain measures plasma drug levels (blood)
120 min	VS, DEQ, PANAS, pain measures
150 min	VS, SOWS, DEQ, PANAS, pain measures
180 min	VS, DEQ, PANAS, CPT, HVLT
210 min	VS, SOWS, DEQ, PANAS, pain measures, methadone/buprenorphine administration
240 min to 420 min (buprenorphine) or 480 min (methadone)	VS, DEQ, PANAS, SAFTEE, HCQ-14, Plasma opioid and CBD levels, safety bloods and Lab Assessments (Day 10) Safety monitoring: VS, MMSE, ACES, field test hourly for at least 2 hours after the administration of methadone/buprenorphine → discharge if VS, MMSE, ACES are back to baseline
Follow-up	Safety follow-up by phone 8 hours after the administration of methadone/buprenorphine

\* The same schedule of events (Table 2) applies to the pilot study and the general study, except for time point 0 minutes. The difference is that in the pilot study, participants will receive 400 mg of CBD on the first test session,

800 mg in the second test session, and 1200 mg in the third test session, using dose-escalation and stopping criteria described in this protocol (Section K.1. subsection K.1.1). Conversely, the general study will have a randomized, placebo-controlled design, so participants will be assigned to CBD (400 mg, 800 mg, 1200 mg CBD) or placebo in a random order (Section K.1, subsection K.1.2.).

**K.9. Sample Size Determination and Power Analysis (General Study):** There are no preliminary data on the effects of CBD on individuals with OUD who are receiving MAT, to calculate the sample size for this study. In a recent human laboratory study, CBD, compared to placebo, blocked cue-induced craving with large effect sizes . To detect a more conservative ( $d=0.64$ ) difference in the attentional bias, craving and pain sensitivity paradigm used, using a within-subject design, given  $\alpha = 0.05$  and  $\beta = 0.2$  (80% power), 34 subjects will be required for the general study. We expect this sample size will also allow us to detect CBD-induced changes in cue-induced craving. To achieve this sample size, considering a historical attrition rate of 25%, we will expect to enroll a total of 46 participants (30 methadone and 16 buprenorphine).

**K.10. Data Analysis Methods (Pilot and General Studies):** To preserve the blind, a data entry operator will enter all study data into an electronic database using double data entry procedures. The data will first be scanned for potential outliers and influential observations using graphical and statistical tools. All outcomes will be summarized descriptively and assessed for normality prior to analysis using normal probability plots and Kolmogorov test statistics. Transformations or nonparametric analyses will be performed as necessary. All tests will be two-sided and considered statistically significant at  $\alpha=0.05$ . All analyses will be performed using SAS, version 9.3 (SAS Institute Inc., Cary, NC).

Aim #1: To determine the safety of acute CBD administration (400 mg, 800, 1200 mg) to people with OUD and chronic pain who are on opioid agonist maintenance. Hypothesis #1: Acute CBD administration will be safe and tolerable. Safety of CBD will be assessed with: the SAFTEE for adverse events; the DEQ items “I like the drug effect” and “I want more of the drug I received” for abuse potential; and by percent correct responses/reaction time in the CPT, and delayed recall in the HVLT, for cognitive performance. All safety outcomes will be tabulated, and descriptive analyses will be conducted. Dose conditions will be compared with regards to the frequency and severity of adverse events, abuse potential and cognitive effects. The PI, in consultation with the DSMB, will determine the dose with the best safety profile.

Aim #2: To determine if CBD (400, 800 mg, 1200 mg) vs. placebo reduces pain sensitivity and attentional bias for opioids and cue-induced craving, elicited by visual probes. Hypothesis #2: The CBD dose required to reduce pain sensitivity and cue-induced craving will be between 400 and 1200 mg. We will fit separate mixed-effects models for each outcome measure. The models will include the within-subject factor drug (CBD 400 mg, 800 mg, 1200 mg or placebo), time of assessment, and interaction between these terms. We will also consider order effects for experimental session day (1, 2, 3 or 4) and several different correlation structures for the repeated measures within individuals and will select the best fitting one based on Schwartz Bayesian information criterion. We will also explore the effects of potential covariates including sex, cannabis use frequency, opioid withdrawal severity, plasma opioid levels, and affective states. SAS PROC MIXED will be used for the mixed-model analyses .

Exploratory Aims: Linear mixed models will be used to assess sex differences, and if CBD is more effective than placebo in the exploratory outcomes.

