**K.1.2 General study:** This is a double-blind, randomized, placebo-controlled, cross-over human laboratory study. Thirty-four male and female participants with OUD on MAT will be asked to arrive at approximately the same time each morning, coordinating with attendance at their opioid maintenance clinic. Participants will be stratified based on whether they are receiving methadone or buprenorphine. This will ensure that the safety and efficacy of CBD can be tested in each arm. On test days, all participants will be asked to refrain from caffeine, nicotine, and will be fasting on the test days. A study nurse will confirm with their respective program that participants did not receive either methadone or buprenorphine that morning and will call the program when testing is complete to permit dispersal of that day's methadone or buprenorphine dose. Participants will undergo a variety of cognitive and self-report measures, as well as assessments to confirm restraint from illicit drug use and lack of adverse effects of medication. Participants are asked to have blood draws during testing session, but this is optional. Participants who give permission to have this blood drawn will have an IV placed will have it placed the morning of each test session. If a subject chooses not to have an IV, only safety bloods will be drawn. Prior to their daily methadone or buprenorphine dose and thus at trough plasma levels of opioid, participants will receive CBD (400 mg, 800 mg, 1200 mg) or placebo, over a total of four sessions. Subsequently, all participants will undergo laboratory testing of measures relevant to vulnerability to relapse, including physiological, subjective, and cognitive outcomes. Participants will be observed for at

least 6 hours after the administration of CBD/placebo, and for 2 hours after the administration of buprenorphine/methadone. In case participants experience any sedation beyond these time points, observation will continue, —consistent with procedures in our research clinic (HSS #JD002). The order of study medication administration will be counterbalanced to reduce perceived bias of study participants and staff.

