This process will involve careful explanation of the consent form by a member of the research staff. Non-research clinicians will be involved in the process when available.

**K.4. Justification of Cannabidiol Dose and Administration (Pilot and General Studies):** FDA-approved Cannabidiol, produced under Current Good Manufacturing Practice (cGMP), will be obtained from G.W. Pharmaceuticals, as "Epidiolex". The bioavailability of oral CBD is 13-19% and the elimination half-life is 56-61 hours . CBD is metabolized primarily in the liver, through the enzymes CYP3A4, UGTA7, UGTA and UGT2B7 isoforms . Importantly, CBD has a wide safety margin and was well-tolerated when co-administered with fentanyl, a high-potency opioid, in humans . The product will be stored in the VACHS research pharmacy as per package instructions. The research pharmacy will prepare CBD oil-based solutions and matching placebos, which will be administered by mouth by the study physician or nurse. CBD will be administered 24 hours after the last methadone/buprenorphine dose. A new IND is being pursued specifically for this project.

CBD is a non-rewarding compound with a wide safety margin . Further, CBD has been shown to produce central effects including hypnotic, anticonvulsive, anxiolytic and neuroprotective effects . CBD has been found to be a potent non-competitive inhibitor at CB-1 and CB-2 receptors  in addition to an allosteric modulator at kappa-opioid receptors, normalizing glutamatergic impairments induced by heroin self-administration . Moreover, CBD has been used in large clinical trials investigating its antipsychotic potential without significant adverse events .

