such that the pharmacokinetics of CBD can vary widely, often without alteration in clinical effects. For instance, administering CBD with food may alter its pharmacokinetics, without significant change in its clinical effects: Among adults with epilepsy, in the fed state, the average Cmax of CBD was 14 times higher, and the AUC0 - ∞ was 4 times higher, compared to the unfed state; conversely, the antiseizure, neuropsychological, and safety profile of CBD remained unchanged in both conditions . Fourth, the relationship between the clinical – or pharmacodynamic – effects of drugs and their pharmacokinetic properties are often non-linear. This is especially true for highly lipid soluble drugs like cannabinoids, including THC and CBD. For example, although THC metabolites stay in the organism for several days or weeks – THC's elimination half-life ranges from 25 to 36 hours –, clinical effects like analgesia or sedation last only several hours.

As a result, cannabinoids like THC and CBD are often administered twice daily when used clinically, rather than once every 3 to 4 days, as if the pharmacokinetic and clinical effects were linear. We have an ongoing randomized, placebo-controlled, within-subject human laboratory study administering single doses of oral THC (10 mg or 20 mg) to persons with opioid use disorder treated with methadone, also has an interval of 72 hours between test sessions.

The latter study has been recently reviewed and approved by the VA HSS (MS0056) and the Yale IRB (Protocol # 2000027065; NCT04025359). Fifth, prior studies conducted at our center suggest that a longer interval is likely to increase attrition of the study population – persons with comorbid opioid use disorder and chronic pain –, such that data collection may be compromised. Finally, we are considering the pharmacokinetic effects of CBD on the main study outcomes, as exemplified by the repeated measurements of CBD and opioid levels in our protocol. Notably, both the FDA and NIDA are in accordance with the proposed interval of 72 hours.

For the general study Research Pharmacy will create a randomization sheet for this general study. Both the research team and participants will be blind to the randomization.

An Environmental Assessment is not required because the action requested qualifies for a categorical exclusion per 21 CFR 25.31(e). To the applicant's knowledge, no extraordinary circumstances exist per 21 CFR 25.15(d).

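### Aim 2 does not fix session as a model term, and does not say which contrast tests CBD or how the pre-dose attentional-bias and HCQ-14 scores enter it

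*Combined protocol and SAP*

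**What the plan says.** K.10, Aim #2, sets up a separate mixed model for each outcome. The terms are drug at four levels, "time of assessment, and interaction between these terms". Session is handled in one clause: "We will also consider order effects for experimental session day (1, 2, 3 or 4". The section then lists covariates to explore: sex, cannabis use frequency, opioid withdrawal severity, plasma opioid levels and affective states. The list is open-ended, and the pre-dose value of the outcome is not on it. The aim is stated as CBD versus placebo, without saying which model term or time point is the test.

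Table 2 in K.8 shows what is measured. The Baseline row, before dosing, ends "plasma opioid (methadone/buprenorphine) level, TLFB, SAFTEE, DEQ, CPT, HVLT, PANAS, AB, HCQ-14, PCS". The 90 min row reads "VS, SOWS, cue session, AB, HCQ-14, pain measures plasma drug levels (blood". So AB and HCQ-14 are both taken before and after the study dose in every session. HCQ-14 is taken again at 240 min or later, after the opioid dose at 210 min. Pain measures have no entry in the Baseline row.

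D.1 makes pain sensitivity, craving and attentional bias secondary hypotheses, but K.9 sizes the study on them.

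**The concern.** Two choices that affect the result are left open.

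**Session.** Participants repeat the same attention tasks and thermal testing in four sessions over ten days, so practice, habituation or drift would be unsurprising. If session is not in the model, any such trend goes into the residual. A term that is merely to be considered can be kept or dropped after the data are seen.

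**The test for AB and HCQ-14.** The stated model allows at least three readings:
- A drug contrast at 90 min that ignores the pre-dose score.
- The drug-by-time interaction. If Baseline is a level of time, this amounts to comparing change scores.
- The drug main effect averaged over the time points. For AB this includes a row recorded before any drug was given, which halves the effect. For HCQ-14 it also mixes in a row recorded after the opioid dose.

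The readings differ in power and in what they estimate. A fourth analysis, the 90 min contrast adjusted for the pre-dose score, is at least as powerful as the 90 min contrast alone and the change score, but it is not named.

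**Working it through.** **Inputs from the plan.** Two-sided alpha 0.05 (K.10); 34 completers, d=0.64 and 80% power (K.9); AB and HCQ-14 at Baseline and 90 min (K.8, Table 2).

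**Assumptions.** The within-participant correlation ρ between pre-dose and 90 min scores is not in the documents; 0.3, 0.5 and 0.7 are used. Session drift is not given either; 0.1, 0.2 and 0.3 within-participant SD per session are used. Variance is taken as equal at the two times, with no carryover.

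**The plan's own figure.** For one dose against placebo as a paired comparison, power is the noncentral t probability with 33 df and noncentrality dz·√34. At dz=0.64, 80% power needs 22 completers, and 34 give 95.2%. K.9's combination of 0.64, 80% and 34 is therefore not reproduced on the paired reading, and K.9 does not say on which SD its d is scaled. That is a separate matter. Here both sizes are carried: dz=0.495, which gives 80.0% at 34 (noncentrality 0.495 × 5.831 = 2.886), and dz=0.64.

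**Effective standardised effect under each test**
- 90 min score only: dz
- Pre-dose score as covariate: dz/√(1−ρ²)
- Baseline-to-90 min drug-by-time contrast (change): dz/√(2(1−ρ))
- AB drug main effect over Baseline and 90 min: 0.5·dz/√((1+ρ)/2), since the true effect at Baseline is zero

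| Test | effective dz from 0.495 (ρ=0.3/0.5/0.7) | Power | effective dz from 0.64 | Power |
|---|---|---|---|---|
| 90 min only | 0.495 | 80.0% | 0.640 | 95.2% |
| Covariate | 0.519/0.572/0.693 | 83.6/89.9/97.5% | 0.671/0.739/0.896 | 96.7/98.7/99.9% |
| Change | 0.418/0.495/0.639 | 65.8/80.0/95.1% | 0.541/0.640/0.826 | 86.5/95.2/99.7% |
| AB main effect, both rows | 0.307/0.286/0.268 | 41.2/36.6/33.0% | 0.397/0.370/0.347 | 61.3/55.2/50.2% |

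The variance with the covariate divided by the variance of change is (1−ρ²)/(2(1−ρ)) = (1+ρ)/2. This is below 1 for any ρ below 1, so the covariate is the more powerful of the two. Change has less power than the 90 min score alone whenever ρ is below 0.5.

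Using the larger error degrees of freedom of the full crossover model, the dz=0.495 figures become about 82% (90 min only), 85/91/98% (covariate) and 68/82/96% (change). The pattern is the same.

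**Session.** Session numbers 1 to 4 have variance (2.25+0.25+0.25+2.25)/3 = 5/3. If session is not modelled, a drift of δ SD per session multiplies the residual variance by 1+(5/3)δ².

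| δ | Variance ratio | Power, dz=0.495 | Power, d=0.64 |
|---|---|---|---|
| 0 | 1.000 | 80.0% | 95.2% |
| 0.1 | 1.017 | 79.3% | 94.9% |
| 0.2 | 1.067 | 77.4% | 93.9% |
| 0.3 | 1.150 | 74.3% | 92.2% |

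Adding session multiplies the standard error of a dose contrast by 1.0004 with position-balanced sequences, or by 1.0026 in one draw of random orders.

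**The case against.** **The model may already use the pre-dose score.** K.10 commits to drug by time, and Table 2 has a Baseline row for both measures. If Baseline is a level of time, the interaction uses it. This stands, and it is why the plan cannot be said to discard the baseline. What remains is that K.10 does not say so, and that the resulting change contrast is the weaker use of the data.

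**No one has said the main effect is the test.** This also stands. The 33-41% figures show what one permitted reading would cost, not what the team intends.

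**Craving already has a before/after measure.** K.6 defines cue-elicited craving as the difference between VAS ratings just before and just after the probe task. That brackets the task within one assessment. It does not settle how the Baseline and 90 min values of AB or HCQ-14 are compared.

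**At the plan's own effect size little changes.** At d=0.64 read as paired, the 90 min score alone has 95% power, and the covariate raises it to 97-99.9%. This stands and limits the weight of the point. So does the secondary status of Aim 2.

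**The stronger reading: carryover.** K.4 states that "the elimination half-life is 56-61 hours", and sessions are 72 hours apart, so 2^(−72/56) to 2^(−72/61), or 41-44%, of the drug could remain. A reader might infer biased dose contrasts, or sequences that must be rebuilt to balance the preceding dose. The documents do not support that. K.4 argues that effects do not track residual drug, and cites a CBD study with 3-4 day intervals (at 400 and 800 mg, so not reaching 1200 mg) and FDA and NIDA agreement. On sequences, K.1.2 says "The order of study medication administration will be counterbalanced to reduce perceived bias of study participants and staff", the Table 2 footnote says "participants will be assigned to CBD (400 mg, 800 mg, 1200 mg CBD) or placebo in a random order", and K.4 says "Research Pharmacy will create a randomization sheet for this general study". How the sheet is built is not shown, so it cannot be called unbalanced. Nor would a single Williams square be a complete safeguard: it shrinks all doses equally only if carryover stops at the immediately preceding dose. If earlier doses decay at the same rate, its contrasts can differ, for example 0.81/0.87/0.85 of true.

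**Conclusion.** The point holds in a limited form, as something to consider. K.10 leaves the session term optional and leaves open the term, time point and use of the pre-dose score that define the Aim 2 test for AB and HCQ-14. Neither part requires any assumption about carryover.

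At dz=0.495, naming the covariate-adjusted 90 min contrast gains about 4, 10 or 18 points of power over the 90 min score alone (ρ=0.3/0.5/0.7). Over the change contrast it gains about 18, 10 or 2 points. At d=0.64 the gain over the 90 min score alone is under 5 points. Omitting session costs 1 to 6 points at dz=0.495 and at most 3 at d=0.64, over the drifts assumed.

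The correlations, the drifts and the 0.495 are assumptions; only d=0.64, 34 completers and the assessment schedule come from the plan. The documents do not show that any dose contrast is biased, that carryover is present, or that the allocation sequence is deficient.

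**What to change.** Before unblinding, amend K.10, Aim #2:

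1. Include session number (1 to 4) as a fixed effect in every Aim 2 model.
2. For AB and HCQ-14, name the dose-versus-placebo contrast at 90 min as the test. Adjust it for that session's pre-dose score and for the participant's mean pre-dose score, so that the within-participant slope is separated from differences between participants. Report the Baseline-to-90 min drug-by-time contrast as a sensitivity analysis. Report the HCQ-14 assessment after the opioid dose separately.

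Item 2 does not apply to QST, because Table 2 lists no pre-dose pain measures. No change to the session interval, the allocation sequence or data collection is asked for.

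The cost is a few sentences and slightly more analysis work. The gain from item 2 is small if the pre/post correlation is low. That is plausible for HCQ-14, because its Baseline value precedes the cue session. At ρ=0.1 and dz=0.495 the covariate gives 0.495/√0.99 = 0.497, about 80% power, so it adds almost nothing.
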